5.2.1 Stopping Rules

No acute toxicity was seen in the preclinical studies in rats with administered intravenous doses up to 1000 µg (approximately 1500 µg/kg in the rat). Potential toxicities would be those that could occur (1) because of enhanced efflux of K^+ with resultant decreased intracellular Ca^{++} concentration, thus altering smooth muscle function in diverse organ systems; (2) reaction to the naked DNA.

In the event that any participant experiences one of the following events, **no** additional participants will be accrued and **no** further doses of hMaxi-K will be administered until the DSMB and FDA have reviewed the case and have provided their recommendation to the sponsor.

- 1) Urinary retention, i.e., the inability to micturate for more than 12 hours with a urine bladder volume (greater than 400 ml established by bladder scan) that requires placement of a bladder drainage catheter.
- 2) Any adverse event of Grade 2 that last longer than 96 hours or Grade 3 or higher in the blood chemistry, completed blood count or urine categories of adverse event criteria listed in Appendix A.
- 3) In the event of a clinically significant sign or symptom reported by the site PI to the medical monitor in any of the first four participants of each cohort unless permission is given by the medical monitor.
- 4) Bladder pain and /or irritation that persists for four hours or more after gene transfer that is thought by the Principal Investigator not to be related to acute trauma from the cystoscopy, direct bladder muscle injections, and catheterization.

Clinical data regarding the event will be collected, reviewed, and discussed with DSMB and FDA. After review of these data with FDA the clinical study may resume **only** with concurrence of FDA.

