Up to 9 female participants (6 participants on active treatment and 3 on placebo) will be enrolled per dose level “arm”. The 2 active doses to be evaluated sequentially are 16000 µg and 24000µg compared to intramuscular injections into the bladder wall of PBS-20% sucrose (control group). Additional participants may be enrolled for evaluating the tolerability to a given dose. Each arm of 9 participants per dose level will be enrolled sequentially, beginning with the lowest dose. Enrollment of the first 5 participants in each cohort will be managed directly by the sponsor (or their designee) with a 2-day waiting period following each participants dosing. The next participant will be enrolled only after the site has contacted the previously dosed participant on day 3 following transfer to determine if a clinically significant adverse event occurred. The site will contact the clinical monitor with the result of that contact. In the event that no event occurred the next participant will be enrolled. The DSMB will review eligibility and all available safety data after the 5th participant has been administered study drug in the first dosing cohort. This first review will occur as soon as possible after the 5th participant’s 3-Day Post-visit 2 telephone contact. Following their review of the safety data, the DSMB will recommend whether enrollment into the first dosing cohort may proceed. This process will be repeated through the 5th participant in each cohort before the balance of the cohort (4 additional participants) is enrolled. If a clinically serious sign or symptom is reported the medical monitor will contact all the sites and no further enrollment will be done until the medical monitor or sponsor gives permission. In addition, enrollment into the next cohort or arm in the series (at the next highest dose) will be dependent on safety dose-limiting toxicity assessments as per Section 5.2.

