Microscopic RBC (exception is urine sample post-catherization)	6 – 10 RBC/hpf	>10 RBC/hpf	Gross hematuria	-
CARDIOVASCULAR				
Hypertension	Asymptomatic, transient (<24 H) increase by >20 mmHg (diastolic) or >150/100 if previously WNL; not requiring treatment	Recurrent or persistent (>24H) or symptomatic increase by >20 mmHg (diastolic) or to >150/100 if previously WNL; may require monotherapy	Requiring more than one drug or more intensive therapy than previously	Life-threatening consequences (e.g., hypertensive crisis)
Hypotension	Transient orthostatic hypotension, intervention not indicated	Symptoms corrected with oral fluid replacement	IV fluid required; hospitalization not required	Hospitalization required
Conduction abnormality/atrioventricular heart block	Asymptomatic, no intervention indicated	Non-urgent medical intervention indicated	Symptomatic & incompletely controlled medically or controlled with device (e.g., pacemaker)	Life-threatening
Prolonged QTc interval	Asymptomatic, QTc interval 0.45 – 0.48 sec	Asymptomatic, QTc interval >0.48 sec	Symptomatic	Life-threatening (e.g., arrhythmia associated with CHF, hypotension, syncope, shock)
Supraventricular & nodal arrhythmia	Asymptomatic, no intervention indicated	Symptomatic, but not requiring treatment	Symptomatic & incompletely controlled medically or controlled with device (e.g., pacemaker)	Life-threatening (e.g., arrhythmia associated with CHF, hypotension, syncope, shock)
Ventricular arrhythmia	Asymptomatic, intervention not indicated	Symptomatic, but not requiring treatment	Symptomatic & incompletely controlled medically or controlled with device (e.g., pacemaker)	Life-threatening (e.g., arrhythmia associated with CHF, hypotension, syncope shock)
Cardiac Arrhythmia – Other	Asymptomatic, not requiring treatment	Symptomatic, but not requiring treatment	Symptomatic, and requiring treatment of underlying cause	Life-threatening (e.g., arrhythmia associated with CHF, hypotension, syncope, shock)
Cardiac ischemia/infarction	Asymptomatic arterial narrowing without ischemia	Asymptomatic and testing suggests ischemia	Asymptomatic ischemia (angina) or testing consistent with ischemia, intervention indicated	Acute myocardial infarction

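### The stopping rules in 5.2.1 do not name Grade 3-4 cardiovascular events or death, so for later participants in each cohort no text makes DSMB and FDA review a condition of restarting

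*Protocol*

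**What the plan says.** Protocol 5.2.1 is a closed list. If any participant has one of four events, no one else is accrued or dosed until the DSMB and FDA have reviewed the case. It adds that "After review of these data with FDA the clinical study may resume" only with FDA's concurrence. The four rules are:

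- Rule 1: urinary retention needing a catheter.
- Rule 2, which has two limbs. The one on duration reads "Any adverse event of Grade 2 that last longer than 96 hours". The other, on severity and by category, reads "Grade 3 or higher in the blood chemistry, completed blood count or urine categories of adverse event criteria listed in Appendix A".
- Rule 3: a clinically significant sign or symptom "in any of the first four participants of each cohort unless permission is given by the medical monitor".
- Rule 4: bladder pain or irritation lasting four hours or more and not attributed to procedural trauma.

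Appendix A grades four groups of events: hematology, chemistries, urinalysis and cardiovascular. The cardiovascular group includes rows such as "Conduction abnormality/atrioventricular heart block" and runs to life-threatening arrhythmia and acute myocardial infarction at Grade 4.

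Outside 5.2.1, protocol 3.1 provides that after a clinically serious sign or symptom in any participant "no further enrollment will be done until the medical monitor or sponsor gives permission". The dose-selection section and SAP 4.1 repeat this.

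**The concern.** Safety is the primary objective and ECG is one of the safety outcomes. Section 5.2.1 itself names, as a potential toxicity, a change in potassium and calcium handling "thus altering smooth muscle function in diverse organ systems". Yet the rule that forces outside review is strictest for laboratory values and says nothing about the gravest clinical events.

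Take participant 6 of a cohort. A Grade 3 platelet count (25,000-49,999 or above 600,000 per mm³ in Appendix A) halts the whole trial until FDA concurs. A Grade 4 ventricular arrhythmia or a death in the same woman, unless it also meets another 5.2.1 rule, is held only by a pause that the medical monitor or sponsor may lift. In a small dose-escalation study of a gene product, that is the decision one would least want to leave to the sponsor's discretion.

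**Working it through.** The plan gives no figure to reproduce. The check compares texts and then counts.

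**1. What the Grade 3+ limb of rule 2 leaves out.** Rows in Appendix A: hematology 7, chemistries 20, urinalysis 2, cardiovascular 8. Total 7 + 20 + 2 + 8 = 37. Counting the whole hematology section as blood count, the limb covers 29 rows and omits 8 (8/37 = 21.6%). This describes the table and does not measure risk. Death has no grade in Appendix A or in protocol 9.5. It appears only as a criterion for a serious adverse event in 9.3.

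**2. Two readings of rule 2.** If the Grade 2 clause covers all adverse events, a Grade 2 cardiovascular event lasting over 96 hours stops the trial, while a Grade 4 one, by the words, does not. If the category list limits both clauses, neither stops it. A Grade 3-4 cardiovascular event is outside the rule either way.

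**3. Whether another provision closes the gap.**

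| Provision | What it does | DSMB and FDA review required before restart? |
|---|---|---|
| 5.2.1 rule 3 | Halt; participants 1-4 of each cohort | Yes, unless the medical monitor waives it |
| 3.1, dose-selection section, SAP 4.1 | Enrollment pause; any participant | No; medical monitor or sponsor lifts it |
| 5.2.2, event-triggered review | DSMB reviews events that would stop the study under 5.2.1 | Carries over the omission |
| 5.2.2, extra meetings | Held if the DSMB asks | No hold |
| 7.14 | DSMB reviews serious adverse event data, possibly only where code-breaking is in question | No timing, no hold |
| 9.6, reporting | Serious adverse events go to FDA and others | No hold |
| 9.6, ECG monitoring | Blood sample and cardiologist for marked QTcF change | No hold |
| 3.1, 11.3 | DSMB review after participant 5's day-3 call | DSMB only, at that point |
| 5.2.2, 11.3 | DSMB review 4 weeks after the cohort's last participant | DSMB only, at that point |

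**4. Who is affected, with 9 planned per cohort and 2 cohorts.**

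- Rule 3 reaches 4 × 2 = 8 of 18.
- Participants 6 to 8 fall outside rule 3, can be followed by further doses in the same cohort, and have no scheduled DSMB review first: 3 × 2 = 6 of 18 (33%). With 12 of 18 on active drug, 6 × 12/18 = 4 are expected on active.
- Participant 5 joins them for events after the DSMB review that follows her day-3 call: (3 + 1) × 2 = 8 of 18 (44%).
- Participant 9 has no one dosed after her in the cohort. In cohort 1 the week-4 DSMB review precedes escalation. Cohort 1 events in participants 5 to 9 that arise after that review are again outside any scheduled check until the fifth participant of cohort 2.

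**5. Doses that could follow if the pause were lifted, before the next scheduled DSMB review.** After an event in participant 5, 6, 7 or 8: 9 − 5 = 4, 9 − 6 = 3, 9 − 7 = 2 and 9 − 8 = 1. After a late cohort 1 event: at most 5, the first five of cohort 2. These are upper limits. They assume dosing one at a time in number order and no replacements, whereas the text requires staggering only through participant 4 (dose-selection section) or 5 (3.1).

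**The case against.** The strongest reply is that a hold already exists. The pause in 3.1 applies at all sites and to any participant, and a Grade 4 arrhythmia plainly qualifies. FDA would be told of a serious adverse event, 7.14 can be read as sending all such data to the DSMB, and the DSMB may call a meeting. Harm would require the medical monitor or sponsor to restart before hearing from either body, and no text tells them to. All of this stands, and it sets the limits of the point.

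Cardiac risk is also screened and watched. Protocol 4.3 excludes recent arrhythmia, infarction, heart failure and QTc of 450 ms or more. ECGs are taken at 2 hours and at weeks 1, 4 and 24 with central reading. Section 1.3 expects no cardiac effects, and the earlier AV block and placebo palpitations were mild and would not have met a Grade 3 rule. This makes an event less likely, but it does not explain why a platelet count should need FDA concurrence and a death should not.

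A reader might infer more in three ways:

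- That from participant 5 on, dosing continues without review. The documents do not support this: the pause covers everyone, and scheduled DSMB reviews cover participant 5's first days and the step from cohort 1 to cohort 2.
- That the plan ignores a known cardiac hazard. The prior data described do not show one.
- That the gap carries a calculable probability of harm. The documents give no rate of Grade 3-4 cardiovascular events or deaths, so any such figure would be assumed.

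**Conclusion.** The point holds as a gap in who must review before restart. Section 5.2.1 is the only text that makes DSMB and FDA review a condition of resuming. Its Grade 3+ limb omits the cardiovascular section, and no rule names death or a life-threatening event. The one rule broad enough to catch them stops at participant 4 and can be waived. The gap falls chiefly on participants 6 to 8 of each cohort (6 of 18), and less on participant 5 after the DSMB's first review and on late cohort 1 events.

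This rests on reading 5.2.1 as a closed list, on the planned 9 per cohort, and on the event not also meeting another rule (for example through a Grade 3 chemistry value). FDA's powers outside these documents are not considered. It is a cheap improvement to a safety rule and affects no analysis.

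**What to change.** Keep rule 2's present triggers for chemistry, blood count and urine. Leave its Grade 2 clause no narrower than now; if the ambiguity is tidied, use the broader reading. Then add a fifth rule to 5.2.1:

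*Any death, any life-threatening serious adverse event, or any Grade 3 or higher event in the cardiovascular category of Appendix A, in any participant, that is not clearly unrelated to study drug or the administration procedure.*

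The procedure has to be named because protocol 9.4 defines unrelatedness for study drug only. The filter is needed because Grade 3 hypertension is defined as "Requiring more than one drug or more intensive therapy than previously", and women on a stable thiazide with other antihypertensives may enroll. Without it, a routine treatment change could halt the trial until FDA concurs.

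State also in protocol 3.1, the dose-selection section and SAP 4.1 that the medical monitor or sponsor pause does not override 5.2.1.

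The cost is wording in these places, with no new data, visits or analyses. The downside is an occasional extra halt pending DSMB review and FDA concurrence, limited by the relatedness filter.

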5.2.2 Dose Escalation

The DSMB will review participant's eligibility data and all unblinded safety data **at 4 weeks** following administration of study drug for the last participant enrolled into each dose cohort, in

order to assess the need for modifications in safety monitoring and/or dosing. Following their review of the safety data for the last participant in the cohort at the 4th week post-dosing, the DSMB will recommend whether or not enrollment into the next dosing cohort may proceed (Section 11.2).

The DSMB will inform the sponsor or designee of their decision to dose escalate in writing.

The DSMB will also review all safety data following the occurrence of any event throughout the study that would stop the clinical study (section 5.2.1) within a reasonable period of time following the occurrence of the event. Additional meetings may be schedule if requested by the DSMB.

The DSMB will review the unblinded safety data from the participants in all the cohorts at the six month timepoint following the final dose.

5.3 Randomization and description of blinding methods

Sites will be provided blinded treatment code identities. For each participant there is supplied a tear off label which should be kept in the participant's source records, affixed to a study treatment label page. This removable panel contains a scratch off laminate which would serve to unblind the treatment if necessary. The DSMB will receive the blinded codes from unblinded statistician.

The treatment code must not be broken by the site unless there is an emergency situation where the appropriate management of the participant necessitates knowledge of the treatment allocation. Every attempt must be made to contact appropriate sponsor personnel prior to breaking any participant's treatment code.

5.3.1 Assigning participants to treatment group

The study is a randomized study with an imbalanced-block design (e.g., 6 active and 3 placebo participants per treatment group). As each participant signs a consent form, they will receive a sequential participant number according to their chronological order of screening within each site. This will be their Screening number. The schedule of randomization numbers and sequence will be generated centrally by the CE3 Inc. Statistical group. This code will be provided to the packaging group (Sharp Clinical Services Inc.) who will package the study drug and blind the random number with a corresponding kit number.

When a participant is qualified for randomization and meets all of the inclusion criteria and none of the exclusion criteria, the site requests a shipment of a study kit from the Clinical Supplies Manager who assigns and ships the next available numbered kit as per the assignment schedule to the site. The kit number allocated will be documented in the participant's electronic case report form (E-CRF) and source notes. This will be the participant's assigned kit number which will be their random number provided by CE3 Inc. Statistical group.

5.3.2 Packaging and labeling

Each participant's assigned kit will contain a two-part (tear-off), label. The label will contain appropriate information including the study number, contents, dosing directions, name of sponsor, storage conditions, packaging lot number, treatment number, visit number. The duplicate portion of this label will be detached and affixed to a page in the source documents as outlined in section 5.1.

5.4 Concomitant Medications/Therapies

Participants will continue any medications they are receiving at study entry for underlying medical conditions with the exception of those described below. All medications taken by participants within 2 months of study entry (including over-the-counter preparations) will be recorded on the Concomitant Medication Form. Any changes in concomitant medication, including additions, discontinuations, and dose changes, occurring during the study will be recorded on the concomitant medication form. If participants are receiving hormone replacement therapy, dosing should be stable for at least 2 months prior to enrollment and remain stable throughout the study.

Participants are not allowed to concomitantly use any approved, unapproved, or investigational medications or therapies intended to treat OAB/UUI. Anticholinergic or antimuscarinic agents are not permitted. These medications/therapies include, but are not exclusively limited to Detrol® (tolterodine), Ditropan® (oxybutynin), Enablex® (darifenacin), VESicare® (solifenacin), Sanctura™ (trospium), ddAVP. In addition, Botox® (Botulinum Toxin A) or related products are not permitted. Use of Myrbetriq® (mirebegrin) is also an exclusion. Agents known to affect urine production output or detrusor function should also be avoided or kept constant throughout the study (if permitted by Sponsor), including: adrenoceptor (alpha1a subtype) antagonists; adrenoceptor agonists (beta2 and beta3 subtypes); phosphodiesterase-1 inhibitors; adenylyl cyclase stimulators; neurokinin receptor antagonists (NK-1, NK-2 subtypes); potassium channel activators; calcium channel blockers; serotonin reuptake inhibitors (serotonin-noradrenalin uptake inhibitors); cyclooxygenase-2 inhibitors. Thiazide diuretics alone or in combination with antihypertensive medications are acceptable if the dose and dose regimen is kept constant throughout the study. All other diuretics will be excluded, unless approved by the Sponsor or their designee prior to the participant's entry into the study. The investigator should consult the Trial Monitor for any specific questions related to concomitant medication initiation or change. Participants should not take any antiplatelet including over the counter NSAIDs and/or anticoagulant drugs for at least 10 days prior to the treatment visit.

6.1 Outcome Assessments and Procedures

6.2 OAB / DO Objective Assessment: Cystometry

Clinical assessment of the efficacy hypothesis that *h*Maxi-K will reduce detrusor overactivity. Detrusor overactivity will be assessed with two standardized, sitting position, saline cystometries followed by pressure flow studies (see **Appendix D**). Every attempt should be made to perform the studies at the same time of day and in the same way for each participant. Studies are to be completed at V1A (screening), V5 (4 weeks post dosing with study drug) and V8 (or Final Visit).

An over-reader will interpret the results as well as the investigator. If there is a discrepancy between the reads, then the central over reader's interpretation will take priority.

Table 7: Cystometry Parameters and Definitions		
Parameter	Description	Definition
DO; Yes/No	Detrusor overactivity ≥ 5 cm H ₂ O	Any involuntary contraction that has a pressure ≥ 5 cm H ₂ O (INCLUSION CRITERIA)
V _{First des} (mL)	Volume at first desire to void	The volume attained during filling cystometry that would lead the patient to pass urine at the next convenient moment but voiding can be delayed if necessary (ICS definition).
P _{det. open} (cm H ₂ O)	Detrusor pressure at beginning of voiding (prior to onset of first contraction (either volitional or involuntary))	Detrusor pressure at onset of the first detrusor contraction (either volitional or involuntary).
V _{1st} (mL)	Volume at first involuntary contraction; if detrusor overactivity (DO) present. Not applicable if no DO present.	Volume infused at the point of maximum detrusor pressure during the 1 st contraction. ¹
Det _{freq}	Total number of detrusor contractions during procedure (voluntary AND involuntary)	Total number of detrusor contractions including voluntary AND involuntary
Leak (Yes/no)	Was there a leak with overactivity	Involuntary detrusor contractions resulting in leak (NOT counting voluntary voids).
DO _{Leak freq}	Number of involuntary detrusor contractions resulting in leak (if DO present)	Number of involuntary detrusor contractions resulting in leak (if DO present). ¹
V _{leak} (mL)	If yes, Volume of each leak	Volume of each leak for each episode of leak ²
V _{leak cum} (mL)	If yes, cumulative volume of ALL leaks during procedure	Cumulative volume of leaks (calculated by computer from individual volumes) ²
DO _{No Leak freq}	Number of involuntary detrusor contractions NOT resulting in leak.	Total number of involuntary detrusor contractions that do not have an associated leak. ¹
P _{det Max} (cm H ₂ O)	Maximum detrusor pressure at involuntary contraction	Maximum amplitude of detrusor contraction during an involuntary contraction (if present) ³
P _{det 1st} (cm H ₂ O)	Maximum detrusor pressure at FIRST contraction	Max detrusor pressure at FIRST contraction (voluntary or involuntary). ¹
P _{Det Any} (cm H ₂ O)	Maximum detrusor pressure at ANY contraction	MAXIMUM detrusor pressure attained during the entire study (voluntary or involuntary). ⁴
Cys Cap (mL)	Cystometric Capacity: Volume at strong urge to void	The volume at which the patient feels that he/she can no longer delay micturition (has a strong desire to void). (ICS definition)
Q _{max} (mL / sec)	Peak flow rate during voiding (for both leaks and voluntary voids)	The Maximum rate of flow during any void (for both involuntary and voluntary voids)
V _{voided} (mL)	Total voided volume (leaks and voluntary)	Total volume voided for leak and volitional voids during the procedure
PVR (mL)	Post Void Residual Volume (PVR) (from catheterization)	Volume left in bladder after voiding at the conclusion of the study. This is measured by urodynamic catheterization.
(V _{total bladder}) (mL)	Total Bladder Volume (Total voided volume +catheterized PVR)	Post void residual volume + total voided volume (will be calculated)

DO _{dur} (seconds)	Duration of detrusor overactivity	Duration of MAXIMUM detrusor activity. ²
--------------------------------	-----------------------------------	---

P_{Det}, Q_{Max} (cm H ₂ O)	Detrusor pressure at maximum flow during an involuntary contraction	Maximum detrusor pressure during terminal void (voluntary or involuntary). ²
$V_{bladder DO}$ (mL)	Bladder volume at each involuntary detrusor contraction	Infused bladder volume at the peak pressure of each involuntary contraction minus the amount leaked at each point for each involuntary contraction; Total will be calculated by the computer. ²
P_{abd} (cm H ₂ O)	Maximum abdominal pressure during any contraction	MAXIMUM abdominal pressure during ANY contraction. This will assess the abdominal straining component to voiding. ²

 1. This is done by overreader, but not the sites 2. Done by site only 3. Detrusor pressure at first involuntary contraction 4. Maximum detrusor pressure at ANY contraction on eCRF. 		
is called “Detrusor Pressure” for sites on eCRF.
 
is called “Maximum Detrusor Pressure” for sites on eCRF.

Digitized recordings should be captured and stored for each patient. Waveforms from filling cystometries and pressure flow studies will be interpreted by a trained professional for each parameter noted above in table. Printed waveforms should be kept with the patient’s source records, with items such as artifacts and peak pressure measurements clearly identified (see details in **Appendix D**).

Table 7. Procedure Flow Guidance on Cystometry Visit Days (and Cystoscopy)

Review diaries, pads, con meds, and AEs; ECG, physical exam, vital signs, QoL assessments, questionnaires	Prior to cystometry
Bladder Scan	Bladder scan at V8 to be done before catheterization for urine culture.
Urinalysis	Prior to cystometry (by Dipstick at Visit 1A)
Urine culture	Prior to cystometry by catheterization and repeat prior to discharge by clean void
Urine/blood for hSlo cDNA detection	Prior to cystometry (not at Visit 1A)
Phlebotomy	Prior to cystometry (not at Visit 1A)
Cystometry	Should be done exactly the same way at each visit
Cystoscopy: Visit 2 Only	

Table 7. Procedure Flow Guidance on Cystometry Visit Days (and Cystoscopy)

Review diaries, pads, con meds, and AEs; ECG, physical exam, vital signs, QoL assessments, questionnaires	Prior to cystoscopy and drug administration
Urine/blood for hSlo cDNA detection	Prior to cystoscopy and drug administration
Urinalysis	Prior to cystoscopy (by Dipstick at Visit 2 prior to drug administration)
Urine culture	Prior to cystoscopy by catheterization and repeat prior to discharge by clean void (first clean void after study drug administered)
Phlebotomy	Prior to cystoscopy
Administer the local anesthesia through a catheter	At Visit 2 only; after all required Baseline procedures completed
Cystoscopy	At Visit 2 only, insert cystoscope 10-20 minutes after local anesthesia given
Study drug administration through a cystoscope	At Visit 2 only, 20-30 injections in bladder wall depending on dose
Blood pressure	BP will be taken every 15 minutes for 2 hour post administration of study drug.
Urine/blood for hSlo cDNA detection; ECG	2-hours post-dosing

